The definitions of the Brazilian Ministry of Health (Brazil, 2020) will be used:

Flu syndrome (GS): Individual with acute respiratory condition, characterized by at least two (2) of the following signs and symptoms: fever (even if reported), chills, sore throat, headache, cough, runny nose, olfactory disorders or taste disorders.

Severe Acute Respiratory Syndrome (SARS): Individual with **GS** sit : dyspnea/respiratory distress OR persistent pressure in the chest OR O2 saturation less than 95% in room air OR bluish coloration of the lips or face.

Confirmed cases of COVID-19:

- **By clinical criterion:** Case of GSs or SRAG with clinical confirmation associated with anosmia (olfactory dysfunction) OR ageusia (gustatory dysfunction) acute without other previous cause.
- **Por clinical - epidemiological criterion:** Case of GSs or SRAG with a history of close or household contact, in the 14 days prior to the appearance of signs and symptoms with case confirmed for COVID-19.
- **By clinical criterion - imaging:** Case of GSS or SRAG or death from Rags that could not be confirmed by laboratory criterion And that presents at least one (1) of the following tomographic changes:
 - Peripheral, bilateral , **horizontal matte glass opacity** , with or without consolidation or visible intralobular lines ("paving"), **OR**
 - **Multifocal frosted glass** opacity of rounded morphology with or without consolidation or visible intralobular lines ("paving"),**OR**
 - **Reverse halo sign** or other findings of organizing pneumonia (later observed in the disease).
- **By laboratory criterion:** Case of SG or SRAG with test of:
 - **Molecular biology:** detectable result for SARS-CoV-2 performed by the RT-PCR method in real time.

- **Immunological:** reactive result for IgM, IgA and/or IgG performed by the following methods: Enzyme-Linked Immunosorbent Assay (ELISA); Immunochromatography (rapid test) for antibody detection; Electrochemiluminescence Immunoassay (ECLIA);

- **Antigen Research:** reagent result for SARS-CoV-2 by immunochromatography method for antigen detection.

- **By laboratory criterion in asymptomatic individual:** Asymptomatic individual with test results:

- **Molecular Biology:** detectable result for SARS-CoV-2 performed by the RT-PCR method in real time;

- **Immunological:** reagent result for IgM and/or IgA performed by the following methods: ELISA or Immunochromatography (rapid test) for antibody detection.

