- From the fourth to the fifth week: ulcer with 4 mm to 10 mm in diameter.
- From the 6th to the 12th week: scar with 4 mm to 7 mm in diameter, found in about 95% of those vaccinated.

Although the response to placebo did not cause any local vaccine reaction, which would question its use, we believe that if we did not use any intervention in the control group, bias could occur, in view of the possible reduction of precautionary measures and care in the use of personal protective equipment (PPE) in the experimental group, believing that they were "protected" by a vaccine, although its effectiveness has not been proven in this situation. On the other hand, those not vaccinated would be more careful in relation to hygiene measures and use of PPE. Using placebo, we believe that we match the usual prevention measures to COVID-19 in the study population at least in the first month of follow-up, a period prior to the onset of the lesions expected by BCG vaccination.

Adverse events:

The definition for an adverse event described in the Manual for Notification of Adverse Events and Safety Monitoring in Clinical Trials (Anvisa, 2016) will be used as a definition for an adverse event: "any adverse medical occurrence in a patient or clinical trial participant to whom a pharmaceutical product has been administered and who does not necessarily have a causal relationship to treatment. As a result, an AE can be any unfavorable and unintentional sign, symptom, or disease (including results outside the reference range), associated with the use of a product under investigation, whether related to it or not. A serious AE shall be considered to have one resulting in any adverse experience with medicinal products, biological products or devices occurring at any dose

and resulting in any of the following outcomes: a) death; b) threat to life; (c) persistent or significant disability/disability; d) requires hospitalization or prolongs hospitalization; e) congenital anomaly or birth defect; f) any suspected transmission of infectious agent by means of a drug or; g) clinically significant event."

Adverse events that do not fall within the definition of severe AE (definition above) will be graduated according to ananvisa 2016 manual:

- Light Level: Problem present less than 25% of the time, with an intensity that a person can tolerate and that rarely happened in the last 30 days;

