Adverse reactions were generally lighter and less frequently reported in the elderly (\geq 65 years of age). Analgesic and/or antipyretic medications (e.g., paracetamol-containing products) may be used to provide relief from adverse reactions after vaccination. Adverse drug reactions (ADRs) are organized by MedDRA Organ System Class (SOC). Within each SOC, the preferred terms are organized by decreasing frequency and then by decreasing severity. The frequencies of occurrence of adverse reactions are defined as: very common (\geq 1/10); (\geq 1/100 to < 1/10); unusual (\geq 1/1,000 to < 1/100); rare (\geq 1/10,000 to < 1/1,000); (1< 10,000) and unknown (cannot be estimated with available data).

Risks:

The safety of BCG revaccination among health professionals will be evaluated in order to describe possible injection site reactions and other adverse events.

In addition, we will minimize the occurrence of AS, excluding immunosuppressed individuals or using concomitant medications that impact immune responses.

Local and systemic AEs will be evaluated at relevant times through medical visits, for example in the first 20 minutes after BCG injections and in later visits, either in person or by telephone contact. The EAs will be noted and graduated according to the ANVISA Manual.

Adverse events to the BCG vaccine, more frequent have been abscess and lymphadenopathy, with higher reports for men than for women. The rates of As per 10,000 distributed doses were from 11.6 to 15.4, respectively. Unsupurated regional lymphadenopathy greater than 3 cm, supurated regional lymphadenopathy, cheloid scar, or lupoid reaction may occur. The EAs will be monitored and handled throughout the follow-up visits.

The research centers will also be open and available for extra views in case of adverse events. The manifestations will be recorded in the data collection instruments and will be treated and monitored in hospitals linked to the research centers. Similarly, the events will be notified to the National Immunization Program of the Ministry of Health, informing the batch of the vaccine applied as well as the event that occurred. Participants will receive all care and will be guaranteed assistance.

Benefits:

The results of this study may help define a form of prevention of COVID-19 for health professionals and in the future in the population as a whole.

LABORATORY PROCEDURES:

Blood collection:

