According to CNS Resolution No. 441 of 2011 (Art. 1) and Ordinance MS No. 2,201 of 2011 (Art. 3), any organized collection of human biological material collected for scientific research purposes, including samples intended for routine examinations in a clinical trial (e.g., blood count and renal function) are considered as constituents of a biorepository or biobank. The biological material will be used as provided for in the research protocol, with no further future analyses different from those foreseen. If there is a proposal for future use of the stored samples, approval in the CEP/CONEP system will be required and a new protocol and TCLE will be submitted so that each participant can choose whether or not to allow the use of the samples for future studies.

Statistical Analysis Plan:

The primary efficacy analysis will compare the cumulative incidence of SARS-CoV-2 infection and the cumulative incidence of severe forms of COVID-19.

These analyses will occur when the last enrolled research subject has completed 30 days and 6 months of preventive treatment and will be performed using the results of COVID-19 diagnostic tests, as well as the data available in participating hospitals and national electronic notification systems of COVID-19. A modified treatment intention analysis (MITT) and protocol (PP) will be performed. The safety and tolerability analysis will consist of all patients who have been randomized and received a dose of the vaccine or placebo. Based on serum immune response concentrations, we will calculate certain immunoinflammatory variables related to the use of BCG versus placebo among subjects infected and not infected by COVID-19 among the categories with COVID-19 vaccine (Coronavac® or Covishield®) and without covid-19 vaccine.

The intervention and control groups will be compared at the time of inclusion in the study in relation to sociodemographic, clinical, radiological and biochemical imaging variables, in order to evaluate the adequacy of the randomization process. Multivariate

analyses using logistic regression or Poisson models with robust variance will be used to evaluate the effect of BCG vaccine on primary and secondary outcomes. Associations will be expressed in the form of risk ratios and respective 95% confidence intervals. Data imputation may be required and the *random forest system* will be used. Statistical software R, version 10.0.

Sample size:

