Regarding the effect of BCG vaccine administration on the cumulative incidence of SARS-CoV-2 infection or on severe forms of COVID-19, a single intermediate analysis will be performed when the number of volunteers included has reached half of the total sample scheduled to verify whether the evidence would already be conclusive and would allow the study to be interrupted. For type I error protection, intermediate analysis will use a Z value of 2.78 (Chow & Liu, 2004).

The analyses that will be performed in the intermediate analysis will be restricted to the following outcomes: accumulated incidence of SARS-CoV-2 infection, cumulative incidence of severe forms of COVID-19 and proportion of serious adverse events.

The following rules will be used to indicate early completion of the study after intermediate analysis:

- Significant difference in the effect of BCG judged by comparing the proportions of patients who develop SARS-CoV-2 infection or severe forms of COVID-19 in each arm of the study;

- If the effect of BCG is similar between groups and there is a significant difference in the cumulative proportion of serious adverse events;

The results will be evaluated by the Data and Safety Monitoring Committee, which will express the need to continue the study, based on the vaccine's performance in terms of the incidences of SARS-CoV-2 infection or severe forms of COVID-19 and adverse events.

Independent Data Monitoring and Security Committee:

The Data and Safety Monitoring Committee (CMDS) will be composed of three members not linked to participating institutions, in accordance with the Operational Guidelines for the Establishment and Functioning of Data Monitoring and Safety Committees of the Ministry of Health (2008).

This committee will be responsible for reviewing the protocol and progress of the study in all centers, with real-time meetings by videoconference, as detailed below, and will consist of:

[name] - Physician - Professor, Faculty of Medicine, Federal University of Rio Grande do Sul

[name] - Statistician - Institute of Collective Health Studies of the Federal University of Rio de Janeiro

[name] - Physician - Professor, Faculty of Medicine, Federal University of Minas Gerais

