An early safety assessment will be carried out when the first 100 participants (approximately 50 per arm) are included. Security data will be reviewed by a CMDS member or someone designated by a CMDS member. In addition, the Committee will review the progress of the study after the inclusion of every 100 additional participants through real-time meetings by videoconference.

CMDS activity plan:

Time of study	Activity	Form
---------------	----------	------

Before the start of the study	Protocol and MOP review	Real-time video conferencing scheduling
During the study	Early safety assessment after inclusion of the first 100 participants	Real-time video conferencing scheduling
	Evaluation of study progression per 100 participants included	Real-time video conferencing scheduling
	Adverse event analysis	Real-time video conferencing scheduling every 2 weeks
	Analysis of serious adverse events	Extraordinary meeting via real-time videoconferencing
	Intermediate analysis after the inclusion of 500 participants	Real-time video conferencing scheduling
At the close of the study	Evaluation of the conduct of the study and its results	Real-time video conferencing scheduling

Plan for monitoring and analysis of adverse events:

The definition for an adverse event described in the Manual for Notification of Adverse Events and Safety Monitoring in Clinical Trials (Anvisa, 2016) will be used as a definition for an adverse event: "any adverse medical occurrence in a patient or clinical trial participant to whom a pharmaceutical product has been administered and who does not necessarily have a causal relationship to treatment. As a result, an AE can be any unfavorable and unintentional sign, symptom, or disease (including results outside the reference range), associated with the use of a product under investigation, whether related to it or not. A serious AE shall be considered to have one resulting in any adverse experience with medicinal products, biological products or devices occurring at any dose and resulting in any of the following outcomes: a) death; b) threat to life; (c) persistent or significant disability/disability; d) requires hospitalization or prolongs hospitalization; e) congenital anomaly or birth defect; f) any suspected transmission of infectious agent by means of a drug or; g) clinically significant event."

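### The interim serious adverse event comparison counts COVID-19 admissions and deaths, which dilutes it as a measure of harm from BCG

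*Combined protocol and SAP*

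**What the plan says.** The section Adverse events, repeated under Plan for monitoring and analysis of adverse events, defines an adverse event as "any adverse medical occurrence in a patient or clinical trial participant to whom a pharmaceutical product has been administered", and counts it "whether related to it or not". Serious events are those that result in "a) death; b) threat to life; (c) persistent or significant disability/disability; d) requires hospitalization or prolongs hospitalization"; the list also covers clinically significant events. The only events taken out of adverse event counting are the expected local BCG reactions (Reaction to BCG vaccine and placebo). COVID-19 is not taken out.

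On efficacy, the Statistical Analysis Plan states: "The primary efficacy analysis will compare the cumulative incidence of SARS-CoV-2 infection and the cumulative incidence of severe forms of COVID-19". Severe forms have no definition of their own. The nearest is the severe acute respiratory syndrome entry in Study Definitions, which rests on clinical signs: "dyspnea/respiratory distress OR persistent pressure in the chest OR O2 saturation less than 95% in room air", or bluish lips or face. Admission and death are not criteria.

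The Interim Analysis Plan compares "accumulated incidence of SARS-CoV-2 infection, cumulative incidence of severe forms of COVID-19 and proportion of serious adverse events". Its second early-completion rule applies when the BCG effect is similar between groups and the cumulative proportion of serious adverse events differs significantly. That proportion is not divided by cause.

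**The concern.** A participant admitted with severe COVID-19 can count once in the efficacy comparison and again in the safety comparison. The safety comparison should show whether the injection harms people. COVID-19 admissions add events to both arms that say nothing about that. If BCG does not affect COVID-19, they add noise. If BCG protects, they also reduce the BCG arm's count and so offset any serious events that BCG causes. In both cases a real excess is harder to see in the comparison that feeds an early-completion rule. Severe COVID-19 already has its own interim comparison, so including it again adds little.

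**Working it through.** **1. The plan's expected infections.** Under Outcomes the plan expects 15, 23, 45 and 38 infections with 376 per arm and 80% vaccinated against COVID-19. These reproduce:
- BCG only: 376 × 0.2 × 0.20 = 15.0
- neither vaccine: 376 × 0.2 × 0.30 = 22.6
- COVID-19 vaccine only: 376 × 0.8 × 0.15 = 45.1
- both: 376 × 0.8 × 0.15 × 0.85 = 38.4 (a 15% relative reduction)

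The implied overall incidence is 0.2 × 0.30 + 0.8 × 0.15 = 18% on placebo and 0.2 × 0.20 + 0.8 × 0.1275 = 14.2% on BCG.

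**2. Infections at the interim.** Half of 752 is 376, or 188 per arm. That gives at most 188 × 0.18 = 33.8 infections on placebo and 188 × 0.142 = 26.7 on BCG. The interim is triggered by inclusion, so many participants will have less than 6 months of follow-up and the true counts will be lower.

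**3. COVID-19 serious events.** The documents give no admission rate and no background serious event rate. Assume that a fraction h of infections becomes serious, and that the non-COVID background is 1% or 3%. The COVID-19 share of placebo serious events is 0.18h / (background + 0.18h).

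| h | COVID-19 serious events, placebo | Share, 1% background | Share, 3% background |
|---|---|---|---|
| 2% | 0.7 | 26% | 11% |
| 5% | 1.7 | 47% | 23% |
| 10% | 3.4 | 64% | 38% |
| 20% | 6.8 | 78% | 55% |

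COVID-19 events are the majority only if h exceeds 0.01/0.18 = 5.6% (1% background) or 0.03/0.18 = 16.7% (3% background).

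**4. Effect on power.** Assume 188 per arm, 1% background, a BCG-caused excess of 5 percentage points and full follow-up. The serious event probability is 0.01 + 0.05 + h × (BCG infection incidence) on BCG and 0.01 + h × 0.18 on placebo. Power is the exact binomial probability that the pooled two-proportion Z reaches the limit with BCG worse. The plan does not say whether its Z of 2.78 also governs serious adverse events, so both limits are shown.

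| COVID-19 events | Z = 1.96, no BCG effect (18% v 18%) | Z = 2.78, no BCG effect | Z = 1.96, BCG protects (14.2% v 18%) | Z = 2.78, BCG protects |
|---|---|---|---|---|
| left out | 80% | 42% | 80% | 42% |
| in, h = 2% | 75% | 37% | 74% | 36% |
| in, h = 5% | 68% | 31% | 66% | 28% |
| in, h = 10% | 59% | 25% | 54% | 21% |
| in, h = 20% | 48% | 18% | 38% | 12% |

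The committee's activity plan puts the interim at 500 participants instead. At 250 per arm, with h = 10% and no BCG effect, power falls from 91% to 72% (Z = 1.96) or from 63% to 38% (Z = 2.78).

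**5. Toxicity at the documented rate.** The Risks section states: "The rates of As per 10,000 distributed doses were from 11.6 to 15.4, respectively". For 188 doses this is 188 × 11.6/10,000 = 0.2 to 188 × 15.4/10,000 = 0.3 events, not all of them serious. The 5-point excess in step 4 is 500 per 10,000, about 32 to 43 times that rate.

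**The case against.** A reader might infer that COVID-19 hospitalisation or death is itself the efficacy outcome. The documents do not say so. The outcomes are infection and severe forms, and the nearest definition uses clinical signs. The events overlap but are not the same.

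A reader might also infer that endpoint events swamp the safety comparison. No figure in the plan supports that: the share runs from about 11% to 78% over the assumed ranges. The upper end may also be too high. Of the 121 expected infections, 83 (45 + 38) are in people vaccinated against COVID-19, and the section on specific vaccines reports no serious or severe cases among vaccinated people (for one of the two products, from 21 days after vaccination). If only infections without COVID-19 vaccination can become serious, the interim has at most 188 × 0.2 × (0.30 + 0.20) = 18.8 of them. At 2% to 10% that is 0.4 to 1.9 serious events in both arms together. Dilution would then sit towards the mild end of the table.

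The third tempting reading is that the trial would miss BCG toxicity. The plan does not rely on this proportion alone. Serious events go to the monitoring committee immediately, adverse events are reviewed every two weeks, suspected-related serious events are reported separately, there is a safety look after the first 100 participants, and the committee may recommend stopping without a formal rule. Small numbers also limit the comparison more than the definition does. All of this stands.

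It can also be said that the safety rule applies only when the BCG effect is similar between groups, so the offset from a protective effect falls outside it. This holds only in part, because similar is not defined. At the expected interim counts of 34 v 27, the difference is 7/188 = 0.0372, the pooled proportion is 61/376 = 0.162, and Z = 0.0372 / √(0.162 × 0.838 × 2/188) = 0.98. If similar means not significant, a truly protective BCG would usually still come under the rule.

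**Conclusion.** The concern holds in a limited form. The plan counts COVID-19 admissions and deaths in the serious adverse event proportion of an early-completion rule, and this lowers the power of that comparison in every scenario run. With no BCG effect on infection, the loss at Z = 1.96 is from 5 percentage points (h = 2%) to 32 (h = 20%), and at Z = 2.78 from 5 to 24. A protective effect makes it larger.

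These sizes depend on the assumed 1% background, 5-point excess and range for h, none of which is in the documents, and on full follow-up, which the interim will not have. At the documented BCG rate the comparison would detect nothing under either definition. What is lost is some ability of one aggregate comparison to show a large, unexpected excess. That does not undermine safety oversight of the trial; it justifies a cheap improvement.

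**What to change.** In the Interim Analysis Plan, define the safety comparison as the proportion of participants in each arm with a serious adverse event other than confirmed COVID-19. Show COVID-19 serious events on a separate line by arm, and keep all-cause serious events as a supporting table. Make the same change to the safety and tolerability analysis in the Statistical Analysis Plan, so that the final report matches. Reporting duties to the regulator and ethics bodies stay as they are.

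The same edit should state which critical value applies to the serious adverse event comparison and what a similar BCG effect means. Two pairs of statements also need reconciling: an interim at half the sample against one at 500 participants, and the serious adverse event rule against the statement that no formal safety stopping rule will be adopted.

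The cost is a sentence in each of the two sections and extra rows in the tables, with no new data collection. Nothing is lost, because the all-cause table remains. The one real burden is that each admission must be attributed to COVID-19 or not. That goes slightly beyond diagnosing infection and severity for the endpoint, and it should be done blind to arm.
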